We propose a novel social support intervention that circumvents all of these barriers, tentatively called *Let's Do Addiction Recovery Together* (*LDART*). Individuals in early recovery will receive a short prerecorded video every night for a month, contingent on them meeting their recovery goal for the day (e.g., not drinking, attending a support group meeting). These videos, generated by members of the local ARC, have two purposes: 1) to congratulate and motivate the recoveree on their recovery journey (in an acutely rewarding way, not unlike monetary rewards in contingency management); 2) to introduce and "put a face and a voice" to local recovery support services, thereby reducing informational and psychological barriers to engagement. If the daily recovery goal is not met, they will receive written words of encouragement and information on a recovery support service, albeit in a less engaging and rewarding format. Given that many in early recovery feel socially isolated²⁵, we hypothesize that these videos will be a potent social reward and motivator for reaching one's recovery goals, such as reducing substance use and increasing social support.

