Video collection (SPs): We will recruit up to 50 adults who are involved in or are allies of the addiction recovery community to participate in this study as SPs. This entire process will occur on their own (i.e., without a member of the study team present), but they can email the study team if any questions arise, particularly during the consenting process. Everything they need to do will be on the Qualtrics platform. First, they will be provided information on the study and screened for eligibility. They will then read the information sheet as part of the consenting process and complete a consent quiz. If they agree to participate, they will check a box in Qualtrics indicating so; a copy of the information sheet will be emailed to them. They will also indicate what they consent to regarding how their videos can be used by the study team (e.g., only in this study or in subsequent studies as well, whether they can be shared on the study Twitter page or shown at conferences), and how long they are stored. They will then be guided to record two short videos to motivate people in recovery. The message in this video will be generic (i.e., no SR PHI), as they will have no knowledge of the specific SRs who will view the message. This Qualtrics link will be optimized to work on smartphones, to make it easier to record and upload videos directly from their phone. SPs will be asked to optionally provide their first name, and information on the recovery work they do (e.g., facilitate a support group meeting on Wednesdays at 6pm) and how to access it (e.g., provide the zoom link or physical address of the recovery community center). They will fill in a brief demographic questionnaire which will not be shared with SRs. Finally, they will be asked under what circumstances the study team can contact them (e.g., in the event that their video is selected for use in the intervention, for which they will receive a \$40 gift card, and/or in the event that their video is voted as one of the best-rated, so that the team can send them an additional \$100 gift card as a prize if they were in the top 3 or \$80 if they were 4th or 5th most highly rated.) After our target goal of number of SP videos is collected, we will state on the video-uploading website that we will no longer have financial compensation for uploading videos, but people are still welcome to do so if they desire. For the second round of video-collection, SPs will be compensated with a \$50 gift card if their videos is selected for use in the second iteration of LDART.

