SRs will then receive a reminder email on the day they decide to begin the intervention (SR Day 0 email; Intervention Materials), and will receive their first Qualtrics link via email on the night they decide to start participating in the intervention (Intervention Materials), each night for a month (Intervention Materials). In these links, they will answer whether they met their recovery goal for the day. If they answer yes, a celebratory message from a SP will be shown; if no, an encouraging message from the SP will be shown. Participants will rate on a scale of 0-5 how motivating and supportive they found the message to be with the option of leaving written feedback on the video. Information provided by the SP about the details of the recovery support service they're affiliated with will also be displayed. SRs will then select their recovery goal for the next day (e.g., stay sober, go to a support group meeting). This entire process should take less than 5 minutes to complete each night. They will be compensated a maximum of \$30 during this month, depending on how frequently they engage with the intervention; this will be paid as a lump sum at the end of the intervention. On the last day of the intervention, they will complete a few additional questionnaires on the Qualtrics link (Intervention Materials). This should take less than 30 minutes to complete, and they will be compensated \$30 for their time. They will also be emailed a Qualtrics link with questionnaires one month after the completion of the intervention (SR questionnaires), which should take about 30 minutes to complete, and they will be compensated \$30. In the last questionnaire, SRs will be asked whether they would like to receive a progress report of their time during the study (SR progress report).

Gather feedback (SRs and SPs): Participants who indicate that they can be contacted regarding an optional 30-minute qualitative interview will be emailed after they upload their video (for SPs), and after they complete their 1-month post-intervention questionnaire (for SRs). Participants who consent to being contacted and do not complete their portion of their study may also be contacted, to better understand barriers to completion. This interview will revolve around feedback on, feasibility and acceptability of the intervention, how to improve it, and possible names for the intervention (*QI discussion guide*) for \$20.

SP Flow Diagram

Protocol Number 2000035434

7/23/24 v10

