SR pilot intervention: Upon completion of the pre-screening form, a zoom meeting or phone call will be scheduled with a member of the study team for Visit 1. Participants will first be asked the same questions that they filled in in the eligibility screen to see if their answers match up. This is to verify the authenticity of the potential participant. This visit will first introduce the study intervention to the participant, with the disclaimer that the intervention is not an established form of treatment and that if emergencies arise while participating in the study, to seek treatment or call 911. Then, a member of the study team will go over the consent document if they are interested in participating, getting informed consent via REDCap, and filling in questionnaires about their demographics, substance use, and recovery capital (SR Questionnaires). Their preference for what time to receive emails/text reminders to log onto LDART each night will be recorded. The visit should last no longer than an hour, and participants will be compensated with a \$30 electronic gift card for their time. SRs will then receive an email to a Qualtrics link on the night they want to begin the intervention (SR Day 0, Intervention Materials). On the days immediately before and after using the intervention (i.e., Day 1 and Day 28), participants will complete the Timeline Follow Back for alcohol use and recovery services, which is built into the Qualtrics intervention. Each night for a month, they will open the Qualtrics link to answer to indicate whether they met their recovery goal for the day. If they answer yes, a celebratory message from a SP will be shown; if no, an encouraging message from a SP will be shown. Video messages will be shown on some nights and written ones (i.e., transcription of the video) on others. Participants will rate how motivating and supportive they found the message to be with the option of leaving written feedback on the video. Information provided by the SP about the details of their recovery support service will also be displayed. They will then select their recovery goal for the next day (e.g., stay sober, go to a support group meeting). This entire process should take less than 5 minutes to complete each night. They will be compensated a maximum of \$30 during this time, depending on how frequently they engage with the intervention; this will be paid as a lump sum at the end of the intervention.

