6.2 Method of Assignment/Randomization (if applicable)

N/A

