7.2 Planned Analyses

Intervention: Standard statistical analyses will be used to determine preliminary efficacy (e.g., random effects regression models) of continuously measured primary (percentage of days abstinent) and secondary (percentage of heavy drinking days) outcomes, measured at three time points (prior to intervention, post-intervention, and one-month post-intervention).

Video ratings done by SRs will be correlated with features of the SP videos to determine what components of the videos are associated with the video having motivational and supportive properties. We will only analyze videos in which SPs consent to their videos being used "in research publications where the content of their videos and information is analyzed".

Some examples of video features include the content of the video (e.g., higher proportion of sentences conveying esteem social support), audio (e.g., higher voice pitch variability), and visual (e.g., percent time making eye contact with the camera). To quantify content, videos will be manually transcribed by the PI to extract textual data. This transcript will be de-identified by removing all names of people and recovery organizations. Some examples of types of qualitative analyses that will be performed include content analysis on the textual data using the Social Support Behavior Code (Cutrona & Suhr, 1992) as a coding scheme, where sentences will be labeled as information, network, esteem, and/or emotional support. A text analysis application called Linguistic Inquiry and Word Count (LIWC, Boyd et al., 2022) will also be utilized to characterize the text based on various psychosocial constructs. For example, the word "cried" is classified in the affect category amongst others. Use of self-disclosure or stigmatizing language will be coded in binary (absent/present).

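### The protocol gives no rule for which SP message or format appears on which night, and the rating analysis names no term for night, participant, format or goal status, so message ratings may be mixed with night order

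*Combined protocol and SAP*

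**What the plan says.** Each SR opens a link nightly for 28 days, sees an SP message and rates it. Section 4: "Participants will rate on a scale of 0-5 how motivating and supportive they found the message to be".

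- **Message type** has a rule, in section 6.1: "If they answer yes, a celebratory message from a SP will be shown; if no, an encouraging message from a SP will be shown".
- **Format** does not. Section 6.1 says only "Video messages will be shown on some nights and written ones (i.e., transcription of the video) on others", without a ratio, a sequence or a statement of what decides.
- **Which SP's message comes when** is not stated anywhere. Section 6.2, where an assignment method would stand, is marked N/A. The nightly links are in the Intervention Materials, which the protocol cites but does not reproduce.
- **Section 1.1 describes format differently.** There the video is contingent on meeting the day's goal, and otherwise "If the daily recovery goal is not met, they will receive written words of encouragement and information on a recovery support service".

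On analysis, section 7.2 says "Video ratings done by SRs will be correlated with features of the SP videos to determine what components of the videos are associated" with motivating and supportive properties. It describes correlations between content, audio or visual variables and rating scores, and names no term for night, SR, format or goal status. Section 3.3 makes the identification of well-received video components a secondary objective. Section 4 also offers SPs an extra gift card "in the event that their video is voted as one of the best-rated".

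**The concern.** Ratings given over a month can drift as novelty fades, fatigue sets in or recovery progresses. The SRs who rate late in the month are those still logging in. If every SR sees messages in the same order, each message stays at or near one point in that course, and recruiting more SRs does not average the effect away. A message's mean rating then reflects its content together with its position, its raters and perhaps its format.

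At stake is the analysis meant to guide future content. A feature could look well received because the videos that have it came early, or a real association could be hidden by night-to-night variation. Format adds a separate difficulty: audio and visual features cannot act on a night when only the transcript is shown, yet nothing excludes those ratings from the correlations.

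**Working it through.** The protocol gives no figure to reproduce. Section 7.1 bases the sample size on other pilot studies, without an SD or an effect size. What follows is illustration.

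**From the protocol:** 28 nights (section 4.1), up to 30 SRs (section 4), ratings from 0 to 5 (section 4).
**Assumed:** a linear drift of D points in mean rating from night 1 to night 28; between-message SD 0.3; within-SR rating SD 1.0 unless stated; one common sequence of 28 messages, one per night, rated by all 30 SRs.

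**1. Share of variance in message means due to night order**

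Variance of 28 equally spaced values over range D = D² × (28² − 1)/(12 × 27²) = 0.0895 D². Message variance = 0.3² = 0.09.

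- D = 1: 0.0895/(0.0895 + 0.09) = 50%
- D = 0.5: 0.0224/(0.0224 + 0.09) = 20%

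These shares leave out sampling error. Adding 1.0²/30 = 0.033 to each denominator gives 0.0895/0.2128 = 42% and 0.0224/0.1457 = 15%.

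**2. Effect on a feature correlation when the feature has no true effect**

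The expected spurious correlation is about (feature's correlation with night order) × √(share including sampling error). For a correlation of 0.4 with night order, its size is 0.4 × √0.42 = 0.26 at D = 1 and 0.4 × √0.154 = 0.16 at D = 0.5. A simulation (4,000 runs per cell, ratings drifting down, two-sided 5% test) agrees:

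| Correlation of feature with night | D | Mean spurious r | False-positive rate |
|---|---|---|---|
| 0.4 | 1.0 | −0.26 | 22% |
| 0.4 | 0.5 | −0.16 | 10% |
| 0.2 | 1.0 | −0.13 | 5% |
| 0.2 | 0.5 | −0.08 | 5% |
| 0 | 1.0 | 0.00 | 0.8% |
| 0 | 0.5 | 0.00 | 3.2% |

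The last two rows show the noise: for a feature unrelated to night order, the unmodelled night variance makes the test conservative. With 28 messages, chance alone gives an absolute correlation with night order above 0.2 for 31% of features and above 0.4 for 3.6%.

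Randomising order per SR brings the mean spurious correlation to about 0 and the false-positive rate to about 5% in every scenario. Under the common order, a linear night term does the same when the drift is in fact linear.

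**3. Dependence of a video-minus-transcript difference on the schedule**

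- 14 video nights, then 14 transcript nights: bias = (14/27) D = 0.52 D, which is 0.26 points at D = 0.5 and 0.52 at D = 1.
- Alternating nights: bias = (1/27) D = 0.037 D, which is 0.02 and 0.04 points.

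**4. Precision of that difference if format were randomised by night within SR**

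SE = √[(4 × SD²/m + τ²)/30], where m is the number of rated nights per SR and τ the between-SR SD of the format effect. With 70% of nights rated (m = 19.6) and SD 1.0:

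- τ = 0: SE = √(0.204/30) = 0.082; 95% CI ±0.16 points
- τ = 0.5: SE = √(0.454/30) = 0.123; 95% CI ±0.24 points

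Across SD 1.0 to 1.5, m = 14 to 28 and τ = 0 to 0.5, the half-width runs from 0.14 to 0.34 points. SRs already treated would not contribute, so the interval would be wider.

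**The case against.** The strongest reply is that silence is not evidence of a common sequence. Section 6.2 is a template heading, and in a single-arm pilot N/A most naturally means that participants are not allocated to groups. The Intervention Materials may contain a sound schedule. This stands: a reader might infer that the ratings are confounded, but the documents support only that they may be.

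A reader might also infer that no analysis could separate message from night. That is too strong. Section 7.2 correlates features across messages, and a night term removes a smooth trend. What remains is that such adjustment assumes a shape for the trend, and that none is planned.

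The one-message-per-night model is also a simplification. Message type follows goal status, so even a common sequence can show different messages on the same night. The 20% to 50% is therefore an illustration under an assumed drift, and a share of variance is not itself bias.

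Finally, the prize wording in section 4 does not say that the nightly ratings decide the winners, so no consequence for prizes can be claimed.

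**Conclusion.** The gap is real: the protocol should state how messages and formats are assigned to nights, and the rating analysis should account for night, SR, format and goal status. Under a common sequence, a drift of 0.5 to 1 point and a message SD of 0.3, night order would be about 20% to 50% of the variance in message means before sampling error. The sure cost is noise. Material bias needs a feature that tracks night order fairly closely, which is uncommon by chance. The drift and SDs are assumptions and the schedule is unknown.

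A reader might conclude that the trial has lost its one unbiased comparison of video with text. The documents do not support that. The comparison is not an objective, outcome or planned analysis, so at most an opportunity is missed, and it would concern nightly ratings, not drinking. Nor can randomised format be prescribed while sections 1.1 and 6.1 disagree. If format follows goal attainment, as section 1.1 has it, format and goal status cannot be separated at all. Celebratory versus encouraging messages are tied to goal status under either text, and randomising order does not change that.

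**What to change.** 1. In section 6.2, replace N/A with a rule: for each SR, the order of SP messages is randomised from a pre-generated list, separately within the celebratory (goal met) and encouraging (goal not met) sets. Each list needs to cover 28 nights, since an SR could meet or miss the goal on all of them.
2. Record message ID, night, format and goal status with every rating.
3. In section 7.2, analyse ratings with a mixed model that includes SR, message, night, format and goal status. If format turns out to be set by goal status, the two cannot both be estimated, and the plan should say so.
4. Restrict audio and visual feature analyses to nights when the video was shown.
5. Reconcile sections 1.1 and 6.1 on whether format depends on goal attainment. Only if it does not could format also be randomised by night within SR, with the video-minus-transcript rating difference reported as exploratory.

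The cost is modest Qualtrics programming (a randomiser or up to 30 prepared sequences) and a short amendment, with no extra visits, items or participants. SRs already treated keep the old order and must be flagged. Section 4 foresees a second iteration of LDART, so a prospective change may still be useful.

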6.1.1 Data Collection

Video recordings and information on recovery services from SPs will be collected and stored on Qualtrics, which is a secure site. The majority of data from SRs will be collected via standard and validated questionnaires sent to the participant via Qualtrics. Participants will input their unique ID number when filling in all questionnaires, so all questionnaire data will be de-identified. Qualtrics links for SRs with videos made by support-providers will only be accessible with a valid participant ID and link, which will prevent others from viewing the video.

Qls will be semi-structured using the discussion guide (included in *Supporting Documents*), and recordings of the meeting will be collected using the embedded function in Zoom. Audio transcripts of the Qls will be de-identified (i.e., no names will appear in the transcript, only ID numbers).

6.2 Method of Assignment/Randomization (if applicable)

N/A

6.3 Adverse Events Definition and Reporting

An adverse event (AE) means any untoward medical occurrence associated with the use of an intervention in humans, whether or not considered intervention-related. There are no expected AEs for this study. The PIs will apprise study personnel of all AEs that occur during the conduct of this research project via email as they are reviewed by the PIs. The protocol's research monitor(s), the Yale School of Medicine Office of Student Research, and regulatory and decision-making bodies will be informed of AEs such as a participant threatening harm to themselves or others within 5 days of the event becoming known to the PIs. An AE or suspected adverse reaction is considered "severe" if, in the view of either the investigator or sponsor, it results in any of the following outcomes: death, a life-threatening AE, inpatient hospitalization or prolongation of existing hospitalization, a persistent or significant incapacity or substantial disruption of the ability to conduct normal life functions, or a congenital anomaly/birth defect. Participants who experience a significant psychiatric or medical problem requiring overnight hospitalization at an acute care facility will also be considered as having experienced a severe AE (SAE). All SAEs will result in the completion of an SAE Form that will be submitted to the Yale IRB within 5 days, and events that are serious or life-threatening and unanticipated (or anticipated but occurring with a greater frequency than expected) and possibly, probably, or definitely related require prompt reporting. The procedures for SAE reporting include written documentation related to the adverse event and specific forms detailing the event.

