STUDY PROTOCOL Social Behavioral Template

Piloting a novel social support intervention for addiction recovery

Protocol Number

2000035434

Protocol Version

7/23/24

10

Clinical Trials Registration Number: NCT# NCT06022107

Confidentiality Statement:

Synopsis

Purpose

The purpose of this study is to pilot a novel web-based intervention to help people who engage in hazardous drinking cut down or quit drinking. This intervention will be implemented through Qualtrics, where each night, participants (referred to as "support-receivers") will access a Qualtrics link containing brief written and video encouragement and information generated by people in addiction recovery communities ("support-providers"). The intervention is designed to help the user maintain motivation to not drink in the short-run, and build connections with addiction recovery communities to sustain their recovery in the long-run.

Objectives

This study will first determine feasibility and acceptability of inviting addiction recovery communities to be support-providers and creating content for this intervention. Second, it will determine feasibility and acceptability of individuals who engage in hazardous drinking using this intervention (aka support-receivers), and determine preliminary efficacy of this intervention on alcohol use and engagement in recovery support services. Third, it will correlate characteristics of content created by support-providers with support-receivers' ratings of the content to identify which characteristics are well-received by support-receivers, to guide future content creation.

Study Population

The target support-providers are individuals who are involved in addiction recovery community (e.g., support group meeting facilitators, volunteers at recovery community centers) or are allies of the addiction recovery community. The target support-receivers are adults who engage in hazardous drinking and live in Connecticut.

Number of Participants

We will recruit up to 50 support-providers, and up to 30 support-receivers to use the intervention. This sample size is appropriate for a pilot study. We will recruit a subset of these participants (10 support-providers and 10 support-receivers) to participate in a follow-up qualitative interview.

Study Design

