2.2 Risks

Overall, participation in this study is thought to involve minimal risk. There is some risk that there may be breaches of the SPs' confidentiality, in that SRs may find ways to share or broadcast the videos they receive. However, this is unlikely because i) videos will be uploaded, stored, and viewed via Qualtrics, a HIPAA-compliant platform; ii) the option to download the videos will be disabled; iii) SRs will be provided with explicit instructions to not share these videos with others; iv) SRs will be advised to watch these videos from a private space with no one else around; v) most individuals in the ARC are open and explicit about their involvement in such communities, so in the unlikely event that these videos are shared, no confidential information will likely be released; vi) Their videos, when integrated into the intervention, will only be accessible with a valid participant ID and link, which will prevent others from viewing the videos; vii) SPs will be briefed on these potential risks and can make an informed decision about participating.

There may be breaches of SRs' confidentiality. However, this is unlikely as all information they provide will be de-identified (they will access their videos using their subject ID) and through Qualtrics, which is a secure platform. It is possible that they may experience distress when watching these videos, however, these videos will be pre-screened by the study team for quality control. SRs may experience distress when filling in questionnaires and taking part in qualitative interviews. However, these questionnaires contain minimally (if at all) distressing topics, and the topic of qualitative interviews will be entirely on the intervention, so this is an unlikely risk. Additionally, to mitigate this concern, they will be informed that they can skip any questions for any reason, and there will be the option to "prefer not to answer" on every questionnaire question.

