3.2 Hypothesis

- H1: Collecting videos of support from the addiction recovery community will be feasible and acceptable.
- H2: Recruitment and retention of SRs will be feasible, and SRs will find the intervention to be acceptable.
- H3: There will be a reduction in alcohol use and an increase in engagement with recovery support services by SRs post-intervention relative to pre-intervention.

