5.3 Eligibility Criteria

In order to be eligible for inclusion to be a SP, an individual must meet all of the following criteria:

- 18 years of age or older
- Is fluent in English and has a 6th grade reading level or higher
- Either volunteers/works for a recovery support service that is freely available to people with addiction (e.g., support groups, recovery community centers) or is an ally/supporter of people in recovery.
- Has access to a smartphone camera / webcam and microphone
- Is willing to consent to creating a video recording of themselves that will be seen by others.

In order to be eligible for inclusion to be a SR, an individual must meet all of the following criteria:

- 18 years of age or older
- Is fluent in English and has a 6th grade reading level or higher
- AUDIT score of ≥8
- Has had at least one heavy drinking day in the past month
- Has some desire to cut down or quit their alcohol use
- Has a smartphone or computer with access to internet
- Have a geoIP address which indicates being on the East Coast of USA

Any individual who meets any of the following criteria will be excluded from participation in this study:

- Has vulnerable population status (e.g., pregnant people, prisoners)
- Is at the time of study participation receiving in-patient psychiatric treatment involving hospitalization

Protocol Number 2000035434

7/23/24 v10

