SR pilot intervention: Visit 1 will occur in a password-protected Zoom room or on the phone with a member of the study team. Participants will be advised to have this zoom meeting in a private room. Participants will be asked to show some form of identification (e.g., driver's license) to verify their identity and/or some other proof that they are based in Connecticut (to protect against scammers). This PHI will not be recorded or stored. Each participant will be sent a link to the REDCap consent form (SR compound consent). A member of the study team will explain the research study to the participant, read the IRB-approved consenting document containing details on the study intervention, procedures and risks, and answer any questions that may arise. The participant will have the opportunity to carefully review the consent form and ask questions prior to consenting. The participant will have the opportunity to discuss the study with their family or surrogates or think about it prior to agreeing to participate. Participants will be informed that participation is voluntary and that they may withdraw from the study at any time, even after consenting to participate. They may also choose not to answer any question for any reason. Participants will also be provided with contact information for the study PIs and the IRB in the event they have additional concerns. Participants will then be asked to summarize their understanding of the study and its risks, and the study team member will ensure that they sufficiently understand the study. If the participant agrees to participate, they will electronically sign the consent form on REDCap, and receive an electronic copy of the consent document for their records via email. The study intervention will not be administered prior to receiving informed consent.

Follow-up qualitative interviews: The consenting process will occur over Zoom with a member of the study team.

6 Study Methods/Procedures

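### The protocol expects no adverse events and never names alcohol withdrawal, although dependent drinkers can enrol and the intervention encourages not drinking (cheap improvement)

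*Combined protocol and SAP*

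**What the plan says.** **Expected events and risks.** Section 6.3 (Adverse Events Definition and Reporting) says "There are no expected AEs for this study". Section 8.7 (Data and Safety Monitoring Plan) calls the risks minimal and says that unanticipated problems, adverse events included, are not anticipated. For SRs, section 2.2 (Risks) lists breach of confidentiality and distress from videos, questionnaires or interviews; on the videos it says "It is possible that they may experience distress when watching these videos". Section 6.4 (Reaction Management) deals with distress only, and its response is referral to mental health resources.

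**Who can enrol.** Section 5.3 (Eligibility Criteria) requires "AUDIT score of ≥8", at least one heavy drinking day in the past month, and that the person "Has some desire to cut down or quit their alcohol use". The two exclusions are vulnerable population status and current in-patient psychiatric treatment.

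**What the intervention encourages.** The Synopsis (Purpose) says "The intervention is designed to help the user maintain motivation to not drink in the short-run". Sections 4 and 6.1 give sobriety as an example of a daily goal, and a met goal brings a celebratory message. Section 7.2 makes percentage of days abstinent the primary efficacy outcome. Hypothesis H3 in section 3.2 is milder: "There will be a reduction in alcohol use".

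**Safeguards in the text.** At Visit 1 (section 6.1) staff explain that the intervention is not established treatment and tell SRs to seek treatment or call 911 in an emergency. Under section 5.5 staff also "read the IRB-approved consenting document containing details on the study intervention, procedures and risks", and then "Participants will then be asked to summarize their understanding of the study and its risks".

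**The concern.** The safety sections do not fit the population that the eligibility criteria admit or the behaviour that the intervention rewards. A dependent drinker can enrol, choose sobriety as the goal for the next day, and stop abruptly at home in a study run entirely online or by phone. For such a person the main foreseeable physical hazard is alcohol withdrawal, which can be serious. The protocol names emotional and privacy risks but not this one.

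What is at stake is participant safety and the accuracy of the risk statement that the IRB approves. No endpoint, analysis or sample size is affected. The practical question is whether an SR is told, before starting, that stopping abruptly may itself cause an emergency. The protocol text does not establish that.

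**Working it through.** There is no figure in the plan to reproduce. The check sets the sections side by side and counts.

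**1. Sections that state SR risks or expected events**

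| Section | What it names for SRs | Alcohol withdrawal named? |
|---|---|---|
| 2.2 Risks | Confidentiality, distress | No |
| 6.3 Adverse Events | No expected events | No |
| 6.4 Reaction Management | Distress | No |
| 8.7 Data and Safety Monitoring Plan | Minimal risk, events not anticipated | No |

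Result: 0 of 4.

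**2. Uses of the words withdraw and withdrawal.** Table of contents 1 + section 5.5, support-provider paragraph 1 + section 5.5, SR paragraph 1 + section 6.5 heading 1 + section 6.5 text 2 = 6. All 6 concern leaving the study or revoking consent to use a video; 0 of 6 concern alcohol.

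**3. Can a dependent drinker enrol?** The AUDIT criterion is a floor of 8 with no ceiling. Of the 2 exclusions, 0 concern dependence or past withdrawal. So enrolment is possible. This says nothing about how many such people will enrol.

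**4. Does the intervention encourage stopping?** Yes, through the stated purpose, the example goal and the celebratory message. It does not require stopping: SRs choose a goal each day, the goal may be to attend a support group meeting, wishing to cut down is enough for entry, and an unmet goal still brings encouragement.

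**5. Would a withdrawal episode count as an adverse event?** Yes. The 6.3 definition covers untoward medical occurrences whether or not they are thought to be caused by the intervention.

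**6. Would naming the risk weaken reporting?** Three rules turn on whether an event was expected: prompt reporting in 6.3, Reportable Events in 8.7, and unanticipated problems in 9.4. A fourth does not: 6.3 requires an SAE Form to the IRB within 5 days for every serious event, with no test of expectedness or relatedness. Its definition includes death, life-threatening events and hospitalisation. A serious withdrawal event would therefore still reach the IRB within 5 days after the risk is named.

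Steps 3 to 5 together make withdrawal foreseeable in an SR who stops abruptly after heavy daily drinking. Steps 1 and 2 show that the protocol does not say so.

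**The case against.** The strongest reply is that a warning to participants belongs in the SR consent form, which is not part of the document reviewed. Staff read its risks aloud and ask the SR to summarise them, so Visit 1 offers more than a general emergency instruction. This stands. A reader might infer that SRs are not warned about withdrawal; the documents do not support that, because the place where the warning would most naturally appear cannot be seen. What remains is that 2.2, 6.3, 6.4 and 8.7 are present text, and they do not match the admitted population whatever the consent says.

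A second reply is that the 911 disclaimer covers the case. It does so in part. It tells an SR what to do in an emergency, but not that stopping can cause one or that advice should be sought beforehand.

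A third is that the exposure is limited. This also stands. Entry needs only one heavy drinking day in the past month, goals are self-chosen, and the documents give no rate of dependence or daily drinking. A reader might infer that the study requires abstinence or that many SRs are at risk; neither is supported.

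A fourth is that serious events are captured anyway. That is correct, and so the point does not extend to reporting. But reporting after the event does not warn anyone before it.

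**Conclusion.** The point holds as a cheap improvement. None of the 4 sections that describe SR risks or expected events names alcohol withdrawal. Eligibility admits dependent drinkers, and the intervention encourages not drinking. The statements in 6.3 and 8.7 that no adverse events are expected or anticipated do not fit that combination.

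The conclusion rests on one assumption from general clinical knowledge, not from the documents: abrupt stopping after heavy daily drinking can cause withdrawal. It rests on no estimate of frequency. The number of SRs at risk, out of up to 30, is not given and cannot be derived.

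The severity is moderated by the Visit 1 disclaimer, the reading and summarising back of risks at consent, investigator contact details given to SRs, nightly check-ins, and AUDIT scores collected at screening and Visit 1. None of these, as described, names the risk. The finding does not show that dependent drinkers must be excluded, that the consent is deficient, or that the reporting rules have a gap.

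**What to change.** 1. **Visit 1 disclaimer (6.1).** Add one sentence: *Stopping abruptly after heavy daily drinking can cause alcohol withdrawal, so seek medical advice before stopping and urgent care if you have symptoms.* This is the change that matters most, because it makes sure the warning is spoken whatever the consent says.
2. **Risk wording.** Name alcohol withdrawal as a possible SR risk in 2.2 and 6.4. Replace the sentence in 6.3 with, for example: *Foreseeable adverse events in SRs are emotional distress and, in those who stop abruptly after heavy daily drinking, alcohol withdrawal.* Bring 8.7 into line, for example: *Apart from the foreseeable events named in 6.3, none are anticipated.* Make no claim about frequency, since the documents support none.
3. **Consent.** Check that the SR consent form says the same, and amend it if it does not.

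Leave the reporting rules as they are.

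The cost is one IRB amendment, one spoken sentence per SR, and a less favourable risk statement. There are no new visits, exclusions or assessments. The revision history shows that version 8 added the Visit 1 disclaimer in the same way.
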